## **2.3. Definition of Study Time Points**

For the summarization of demographic and background characteristics, the value of an endpoint will be the last measurement taken prior to the first dose of double-blind study drug during Treatment Period 1 on Study Day 14.

Baseline values will be determined separately for each treatment phase. The baseline values for each double-blind treatment phase will include the last measurements taken prior to or on the date of the first dose of the double-blind study drug, on Study Day 14 and Study Day 84, unless the time of the assessment/event was after the time the dose was administered. Treatment phase day will be defined separately for each treatment phase as

Treatment phase day = Visit Date – Date of 1st dose of double-blind study drug.

Therefore, Study Day 14 and Study Day 84 will be considered Treatment Phase Day 0 (i.e. Baseline) for Treatment Phase 1 and Treatment Phase 2, respectively. Similarly, Study Day 42 and Study Day 112 will be considered Treatment Phase Day 28 for Treatment Phase 1 and Treatment Phase 2, respectively.

### **2.3.1. Reporting Periods for Concomitant Medications and Safety Endpoints**

For adverse events and concomitant medications, and for unscheduled safety assessments (e.g. laboratory measurements), the reporting period for each treatment phase will include all data recorded after the first dose of double-blind study drug up to 14 days after the last dose of double-blind study drug.

## **2.4. Handling of Dropouts and Missing Data**

For the analyses of endpoints that are collected longitudinally, a last observation analysis may be performed by carrying forward the last post-baseline assessment within a treatment phase. In addition, for many of the endpoints, mixed effect model repeated measures (MMRM) analyses will be performed to mitigate the impact of missing data, assumed to be missing at random.

If only a missing or partial date for AEs or concomitant medications is available and a complete date is required for calculations, the following algorithms will be applied:

- For the start date:
  - If year, month, and day are missing then use the minimum of the patient's first visit date or the consent date.
  - If either only month or month and day are missing then use January 1.
  - If only day is missing, impute the first day of the month.
- For the end date:
  - If year, month, and day are missing then use the patient's last visit date.
  - If either only month or month and day are missing then use December 31.
  - If only day is missing then use the last day of the month.
  - Do not expand the record past the patient's last visit.

The original missing or partial date, the imputed complete date, and the indicator variable that indicates which dates were imputed will be retained in the database.

For vital signs and electrocardiograms, for which the time of assessment is to be captured, assessments made on Study Day 14 or Study Day 84 will be assumed to have occurred prior to dosing (i.e. as planned) if the time of the assessment is missing. For adverse events, for which the time of onset is to be captured, adverse events that start on Study Day 14 or Study Day 84 will be assumed to have occurred after dosing if the time of the assessment is missing.

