## **7.2. Adverse Events**

Adverse events (AEs) will be collected from the day the patient gives informed consent until the patient leaves the study. However, if the investigator learns of any serious adverse event (SAE) that occurs within 30 days after the final dose of study drug, that SAE will be collected even if the event occurred after the patient left the study.

TEAEs for each treatment phase reporting period are defined as reported AEs that first occurred or worsened after the first dose of double-blind study drug. Adverse events with an onset date on or after the first dose of double-blind study drug for Period 1 and before the first dose of double-blind study drug for Period 2 will be assigned to the study drug taken during Period 1; adverse

events with an onset date on or after the first dose of double-blind study drug for Period 2 will be assigned to the study drug taken during Period 2.

Treatment-emergent adverse events will be summarized by the number and percent of patients with the event.

Summaries of TEAEs will include the number of patients with at least one TEAE for each treatment arm. When reporting by system organ class (SOC) and preferred term (PT), the reports will present the SOC in alphabetical order; while PTs within the SOC will be presented in order of overall decreasing frequency of occurrence in the GLWL-01 arm. A patient with multiple TEAEs (different PTs) coded to the same SOC will be counted only once for that SOC, but will be counted each time for different PTs within that SOC. A patient with separate events of the same PT (different start/stop dates within a treatment phase) will be counted only once in the frequency tables for that PT.

An overview of all TEAEs will also be provided by treatment group using the types of AEs defined in the following subsections.

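### Partial adverse event start dates are imputed without reference to either first double-blind dose, and SAP 2.3.1 and 7.2 give different Period 1 windows

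*SAP*

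**What the plan says.** SAP 2.4 has one start-date rule for both AEs and concomitant medications:

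- Day missing: "If only day is missing, impute the first day of the month".
- Month missing, with or without day: "If either only month or month and day are missing then use January 1".
- Everything missing: "If year, month, and day are missing then use the minimum of the patient's first visit date or the consent date".

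The only AE rule in 2.4 that mentions dosing concerns clock time: "adverse events that start on Study Day 14 or Study Day 84 will be assumed to have occurred after dosing if the time" is not known. SAP 2.4 also provides that the original partial date, the imputed date and "the indicator variable that indicates which dates were imputed will be retained in the database".

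On windows, SAP 2.3.1 states that "the reporting period for each treatment phase will include all data recorded after the first dose of double-blind study drug up to 14 days", counted from the final double-blind dose of that phase. SAP 7.2 opens by tying TEAEs to that period: "TEAEs for each treatment phase reporting period are defined as reported AEs that first occurred or worsened after the first dose of double-blind study drug". Its next sentence takes AEs with onset from the first Period 1 dose "and before the first dose of double-blind study drug for Period 2 will be assigned to the study drug taken during Period 1".

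Protocol 10.3.1 treats only the first two weeks of washout as follow-up for Period 1, and Protocol 10.3.4 bases safety on the double-blind phase plus follow-up. SAP 2.9 declares a change to the TEAE determination, but it concerns how worsening events are recorded. It mentions neither a longer window nor date imputation.

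**The concern.** For concomitant medications an early start date does no harm. SAP 5 counts a drug started before dosing as concomitant unless it also stopped before dosing. For AEs onset decides everything, so pulling it back to the earliest date can turn an on-treatment event into a pre-treatment one. The SAP leans the other way for comparable gaps: a missing onset time on a dosing day counts as after dosing, and 7.2.2 counts missing relatedness as related. No reason is given for treating a missing day differently.

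The window question needs no missing data. Two programmers following the SAP could produce different TEAE tables from the same complete dates.

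TEAEs are the endpoint of a secondary objective. With the 19 patients anticipated in SAP 2.9, one misplaced event can move an incidence by 1/19 = 5.3 percentage points, if that patient has no other event of the same term in that phase.

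**Working it through.** **Inputs.** First double-blind doses are on Study Days 14 and 84, and phase day 28 is Study Day 42 or 112 (SAP 2.3). Protocol 7.2.1 has drug given at the site on Day 42, so the last dose is taken as phase day 28. The plan's mapping reproduces: 42 − 14 = 28 and 112 − 84 = 28.

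**Windows for Period 1.**
- SAP 2.3.1: Day 14 to Day 42 + 14 = 56, which is 56 − 14 + 1 = 43 days.
- SAP 7.2 assignment sentence: Day 14 to Day 83, which is 70 days.
- Disputed: Days 57–83, 27 days, or 27/70 = 38.6% of the longer window. Of these, 13 are late washout (57–69) and 14 are the second placebo lead-in (70–83).

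**Share imputed before the first dose.** Assume month and year known, day missing, onset uniform, and the first dose equally likely on each of the 365 days of 2018. For a dose on day d > 1 of a month of length m, the onset days from the dose to month end number m − d + 1, and all are imputed to the 1st, before the dose. Summed over d = 2 to m this is m(m − 1)/2.
- Year total: 7 × 465 + 4 × 435 + 378 = 5,373, or 5,373/365 = 14.72 days per start date.
- With the 14-day follow-up (43 onset days): 14.72/43 = 34.2%.
- Double-blind phase only (days 0–28, 29 onset days): a dose on the 2nd of a 31-day month has 30 such days but only 29 are in range, so subtract 7. Then 5,366/365 = 14.70, and 14.70/29 = 50.7%.

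**Period 1 example.** First dose 10 March 2018, true onset 20 March, day missing: imputed 1 March, not a TEAE. True onset 4 April: imputed 1 April, still a TEAE.

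**Period 2.** The same share is imputed before the second first dose. It reaches the Period 1 window under 2.3.1 only if the 1st of the month is at least 28 days before the Period 2 dose, that is, for doses on the 29th to 31st. That is (7 × 6 + 4 × 3)/365 = 54/365 = 0.15 days: 0.15/29 = 0.5%, or 0.15/43 = 0.3% with follow-up. The rest fall in neither window. If the 7.2 assignment sentence is applied alone, all 14.72 go to the Period 1 drug.

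**Other direction, and effect of a first-dose rule.** The same enumeration was run for uniform onset from consent (17 or 42 days before the first Period 1 dose, from Visit 1 at Day −28 to −3 and Visit 3 at Day 14) to the end of the Period 2 window. Windows follow 2.3.1; units are onset days per start date. The right-hand column applies the first-dose rule with no end-date or earlier-record check.

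| | Current rule | First-dose rule |
|---|---|---|
| Period 1 events lost | 14.72 | 0 |
| Period 2 events lost | 14.57 | 0 |
| Moved to the other period | 0.15 | 0.15 |
| False Period 1, onset before first dose | 0 | 11.97–14.72 |
| False Period 1, onset Days 57–83 | 14.57 | 12.43 |
| False Period 2, onset Days 57–83 | 0 | 14.57 |
| **Total misplaced** | **44.01** | **39.12–41.87** |

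Counts against a true 43 + 43 = 86:
- Current rule: Period 1 is 43 − 14.72 + 14.57 + 0.15 = 43.00; Period 2 is 43 − 14.57 − 0.15 = 28.28 (−34%). Together 71.28, or −17%.
- First-dose rule: Period 1 is 43 − 0.15 + 12.43 + (11.97 to 14.72) = 67.25 to 70.00; Period 2 is 43 + 0.15 + 14.57 = 57.72. Together 124.97 to 127.72, or +45% to +49%.

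Of the 14 lead-in days before a dose, 10.55 on average share its month: 10.55/14 = 75%. If every pre-dose AE had been recorded by the dosing visit and that record were used, only the 14.57 false Period 1 days would remain.

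**Sensitivity.** With the last dose one day earlier (phase day 27), the windows are 42 and 70 days, 28 days are disputed, the shares are 52.3% and 35.0%, the totals are 44.1 against 40.0–42.7, and the over-count is +47% to +51%.

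**The case against.** The trigger is probably rare. AE onset is meant to be captured to the clock time, AEs are reviewed at every contact (at most 21 nominal days apart from Day 0 to Day 126), and about 19 patients are expected. Original dates and flags are kept, listings cover the Entered Population, SAEs are listed separately, and SAP 7 plans no statistical analyses of safety. An affected event stays in the database; only its table classification changes. This stands, and it limits the severity.

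The first-dose rule also shifts error more than it removes it, as the table shows. This stands too. Preferring an over-count is a convention, and the documents do not say whether a first-recorded date exists that would allow a real reduction.

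On the windows, 7.2 can be read as using 2.3.1 to define TEAEs and its next sentence only to attribute them. That reading is reasonable and agrees with the protocol, but the assignment sentence then claims Days 57–83 to no purpose. A clarifying line is still needed.

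A reader might go further and infer that the rule hides harm from GLWL-01, or that half of on-treatment AEs are lost. The documents support neither. Sequences are randomized 1:1, so both treatments are affected and the direction is not fixed. The percentages apply only to AEs with a missing day, whose number is not given. Nor are Period 2 events generally credited to the other treatment; under 2.3.1 at most about 0.5% are.

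**Conclusion.** Minor, but wrong as written. The start-date rule ignores both first doses although classification depends on them. About 51% of day-missing double-blind onsets (34% with follow-up) are imputed before the relevant first dose. This assumes uniform onset, known month and year, and a last dose on phase day 28; for onsets in phase days 0–7 the share is 85%. In Period 1, losses and false gains nearly cancel in number under 2.3.1, although the wrong events are counted. The net undercount therefore falls in Period 2. The absolute effect on TEAE tables cannot be stated, because the number of partial dates is unknown and probably small.

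The 27-day difference between 2.3.1 and 7.2 depends on no assumption about missing dates and should be settled before unblinding.

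**What to change.** 1. For AEs only: when the known month and year match those of a phase's first double-blind dose, impute onset to that dose date, unless the end date or an earlier record of the AE shows that it began before the dose. Otherwise use the earliest compatible date, not before consent. The first doses are nominally 70 days apart, so no month contains both. Keep the present rule for concomitant medications.
2. For year-only or fully missing dates that stay ambiguous, write down before unblinding how the period is chosen, since in a crossover that decides which treatment receives the event. Flag these records and show TEAE tables with and without imputed-date AEs.
3. State in 7.2 that TEAEs are limited to the 2.3.1 reporting period, as in the protocol, and list AEs from the end of that window to the first Period 2 dose separately. If the longer window is intended, declare it in 2.9.

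The cost is a few lines of SAP text and programming; the imputation flag already exists. The downside of item 1 is false TEAEs: about 75% of day-missing lead-in onsets would count unless an end date or earlier record excludes them. Item 1 is justified as the conservative direction the SAP already takes for missing onset time and relatedness, not as a material reduction in total misclassification. Worsening events are separate records under SAP 2.9, so the earlier-record check does not suppress them.

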## **2.5. Adjustment for Multiple Centers**

The randomization is not stratified by investigative site, and the variable “site” will not be included in the statistical models by default.

## **2.6. Interim Analysis and Adjustment for Multiplicity**

There are no planned interim analyses for this study, and there is only a single primary efficacy endpoint. Because this is a Phase 2 study, no adjustments for multiplicity will be made for statistical tests of secondary or exploratory endpoints.

## **2.7. Coding of Concomitant Medications and Adverse Events**

Adverse events (AEs) and conditions/procedures from the patients’ medical histories will be coded using the Medical Dictionary for Regulatory Activities (MedDRA™). Concomitant medications will be coded using the World Health Organization Drug Dictionary (WHODD). The versions of these dictionaries used for reporting will be provided in the CSR.

## **2.8. Reporting Conventions**

This section details the general conventions to be used for the statistical analyses. Departures from these general conventions will be provided in the specific detailed sections of this analysis plan. The following conventions will be applied to all data presentations and analyses:

- Data will be summarized by treatment sequence (i.e. Placebo/GLWL, GLWL/Placebo, and Overall) and/or treatment (i.e. Placebo and GLWL) as appropriate :
- Continuous variables will generally be summarized by the number of patients, mean, standard deviation, median, minimum, and maximum. Exceptions to these conventions will be specifically noted. Categorical variables will be summarized by the number and percent of patients within each category.
- All mean and median values will be formatted to one more decimal place than the measured value.
- Standard deviation values will be formatted to two more decimal places than the measured value.
- Minimum and maximum values will be presented with the same number of decimal places as the measured value.
- The number and percent of responses will be presented in the form XX (XX), where the percentage is in parentheses. Percentages will be rounded to the nearest percent. In the case

of a frequency of zero, the frequency and percentage will be presented as 0 rather than 0 (0%).

- All summary tables will include the analysis population sample size (i.e. number of patients) in each treatment group or sequence.
- Date variables will be formatted as ddMMYY for presentation.

## **2.9. Changes to the Planned Analyses**

Note that what is now called the **Evaluable Population** was called the **Randomized Population** in the protocol.

Blood glucose was added to the list of exploratory endpoints.

The determination of a treatment-emergent adverse event has been changed from that in the protocol, because the way adverse events are actually being captured is not as was anticipated. Specifically, an ongoing adverse event that worsens during the study will be captured as a new adverse event, so that adverse events that start during one period of the trial and get worse during a different period of the trial (which defines treatment-emergent) will have separate records that will be summarized separately.

The statistical analyses will be performed as 1-sided tests rather than 2-sided tests as originally planned, because enrollment was stopped prior to obtaining the intended 34 patients. With the anticipated 19 patients, there is at least 70% power for the primary treatment comparison, which is still considered acceptable for a proof of concept trial.

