10.3. Statistical Analyses

10.3.1. General Statistical Considerations

Statistical analysis of this study will be the responsibility of GLWL Research Inc. or its designee.

Efficacy analyses will be conducted on the randomized analysis set. This set includes all data from all randomized patients receiving at least 1 dose of double-blind study drug. Patients will be included in the analysis if they have a postbaseline measurement for the parameter being analyzed. Safety analyses will be conducted on the randomized analysis set. Patients will be analyzed according to the study drug they actually received.

Data will be presented using summary tables by treatment, unless otherwise specified.

Continuous data will be summarized using the mean, standard deviation, median (for selected variables), minimum, and maximum. Categorical data will be summarized as frequency counts and percentages. Figures may be used to support the presentation of selected data.

All tests of treatment effects will be conducted at a 2-sided alpha level of 0.05, unless otherwise stated.

Baseline values will be defined as the last available value prior to receiving double-blind study drug for each double-blind treatment phase.

For the purposes of follow-up analyses, the first 2 weeks of the washout period will be the follow-up for the Treatment Period 1 double-blind treatment phase and the Follow-up Period will be the follow-up for the Treatment Period 2 double-blind treatment phase.

Details related to handling of missing data will be described in the statistical analysis plan (SAP).

Any change to the data analysis methods described in the protocol will require an amendment only if it changes a principal feature of the protocol. Any other change to the data analysis

methods described in the protocol, and the justification for making the change, will be described in the SAP and/or in the clinical study report (CSR).

Additional exploratory analyses of the data will be conducted as deemed appropriate.

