### 1.3. Determination of Sample Size

Approximately 34 patients were planned to be randomized to 1 of 2 treatment sequences (GLWL-01/placebo or placebo/GLWL-01) in a 1:1 ratio. Thirty-four patients would provide approximately 80% power to detect an effect size of 0.75 for the HQ-CT total score using a 2-sided exact paired t-test with an  $\alpha=0.05$ , assuming 10% drop out.

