## **6. EFFICACY ANALYSES**

Efficacy analyses for this study will be based on the findings from two instruments. First, the HQ-CT is a validated tool developed specifically for PWS to capture observations of problematic behaviors related to food. It consists of 9 items, with a 2-week recall period. The scale provides a composite value from 9 questions, each rated on a scale of 0 to 4 units (total range of score of 0 to 36; Fehnel et al. 2015).

Second, the CGIC is a single-item question rated on a 0 to 7 scale directed at the caregiver asking for an assessment of the overall improvement of patients with PWS.

Both of these assessments will be collected longitudinally during the study.

All efficacy analyses will be performed using the Evaluable Population. The method of analysis or statistical technique employed to address missing data will be described separately for each variable. Presentations of efficacy will include the number of patients with data at each time point plus related statistics derived from the analysis.

All statistical tests will be 1-sided.

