## **6.1. Primary Efficacy Analysis**

The primary efficacy analysis will examine the contrast between GLWL-01 and placebo for the post-treatment HQ-CT total score at the end of the double-blind treatment phase.

The primary analysis will be conducted using a restricted maximum likelihood-based, mixed-effect model repeated measures analysis. The model for the primary analysis will include the fixed, categorical effects of sequence, period, and treatment, as well as the continuous, fixed covariate of the baseline Treatment Phase 1 HQ-CT score minus the baseline Treatment Phase 2 HQ-CT score (diff) and the interaction of period-by-diff (Mehrotra, 2014).

An unstructured covariance matrix will be used to model the within-patient errors.

Satterthwaite's approximation will be used to estimate the denominator degrees of freedom. The significance of differences in least-square means will be based on Type III tests using the observed population margins. The analyses will be performed using the SAS procedure PROC MIXED.

The tabular output for these MMRM analyses will present the least squares means, standard errors, and 95% confidence intervals for each marginal main effect. Pairwise contrasts of the least squares means between GLWL-01 and Placebo will also be provided at each time point using LSMESTIMATE statements.

Descriptive statistics for the HQ-CT score and the within-treatment phase changes from baseline will be provided by treatment and time point.

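### Is the SAP's claim of at least 70% power with 19 patients unsupported?

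*SAP*

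**What the plan says.** SAP 1.3 repeats the sample size statement of Protocol 10.1. "Approximately 34 patients were planned to be randomized to 1 of 2 treatment sequences", and that number was to give "approximately 80% power to detect an effect size of 0.75 for the HQ-CT total score using a 2-sided exact paired t-test", with alpha 0.05 and 10% dropout. Neither document says which standard deviation the 0.75 is measured against, or gives a within-patient correlation.

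Protocol 10.3.1 sets the test level: "All tests of treatment effects will be conducted at a 2-sided alpha level of 0.05, unless otherwise stated". SAP 2.9 then records a change to 1-sided tests because "enrollment was stopped prior to obtaining the intended 34 patients", and adds: "With the anticipated 19 patients, there is at least 70% power for the primary treatment comparison". It calls this acceptable for a proof of concept trial. SAP 6 confirms the change ("All statistical tests will be 1-sided") without naming a level. SAP 6.1 keeps "95% confidence intervals for each marginal main effect" and specifies a mixed model adjusted for the difference between the two period baselines, rather than a plain paired t-test.

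**The concern.** The 70% is the SAP's stated ground for calling 19 patients acceptable, and it stands beside a relaxation of the test made because recruitment fell short. A reader trying to verify it meets three gaps.

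- **Unit of the effect size.** On the SD of the paired differences, the plan's own method gives about 98% at 34 patients rather than 80%.
- **Alpha.** The SAP says 1-sided but gives no level, and 95% intervals pair naturally with 1-sided 0.025.
- **Meaning of 19.** It is set against 34, which is a count before dropout. If 19 is also before dropout, the plan's 10% leaves about 17 analysed.

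If these gaps hid an overstatement, the 80% and 70% would not be on the same footing, and a null result would be read with more confidence than the trial can support.

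**Working it through.** **Inputs.** Effect size 0.75, 2-sided paired t-test, alpha 0.05, 34 randomized, 10% dropout (SAP 1.3, Protocol 10.1). 19 patients, 1-sided (SAP 2.9). Assumed, because the documents do not give them: the SD unit, the within-patient correlation ρ, and 1-sided alpha 0.05.

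**Formula.** Power comes from the noncentral t distribution with n − 1 degrees of freedom and noncentrality dz·√n. If 0.75 is in single-score SD units, dz = 0.75/√(2(1 − ρ)). If it is in units of the SD of the differences, dz = 0.75.

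**Step 1: reproduce the plan's 80%.** 34 × 0.9 = 30.6, so 30 completers.
- dz = 0.75: power 97.8%. This does not reproduce 80%.
- Single-score SD, ρ = 0: dz = 0.75/√2 = 0.530, noncentrality 0.530 × √30 = 2.90, power 80.2%. This reproduces it. The smallest n reaching 80% on this basis is 30, and 30/0.9 = 33.3 rounds up to 34.

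**Step 2: carry that basis to 19 patients, 1-sided 0.05.** Noncentrality 0.530 × √19 = 2.31, power 71.9%. With dz = 0.75 it is 93.3%. The statement holds on both.

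**Step 3: take 10% dropout off the 19.** 19 × 0.9 = 17.1, so 17 completers. Power by ρ, with the 34-patient figure for comparison:

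| ρ | 17 completers, 1-sided 0.05 | 30 completers, 2-sided 0.05 |
|---|---|---|
| 0 | 67.3% | 80.2% |
| 0.07 | 70.0% | 82.9% |
| 0.1 | 71.3% | 84.1% |
| 0.2 | 75.6% | 88.1% |
| 0.3 | 80.4% | 91.9% |

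The shortfall at ρ = 0 is 70 − 67.3 = 2.7 points, and it is gone at ρ = 0.07.

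**Step 4: try 1-sided 0.025.** With 19 analysed and ρ = 0, power is 59.0%. At 2-sided 0.05 it is also 59.0%. Moving from one to the other would add no power, yet SAP 2.9 gives the smaller enrolment as the reason for the move. Carrying 0.05 over from Protocol 10.3.1 is the reading that makes sense of the text. The 95% intervals in SAP 6.1 are a display of estimates and set no test level.

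**Step 5: the planned model.** Let r be the correlation between the baseline difference and the outcome difference; the documents give none. For complete cases, regressing the period difference on sequence and baseline difference leaves n − 3 degrees of freedom and scales the residual SD by √(1 − r²). At 1-sided 0.05 and ρ = 0, for r from 0 to 0.5, power is 69% to 80% with 19 and 64% to 75% with 17. At ρ = 0.2 the range with 17 is 73% to 83%.

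**The case for a change.** The strongest case for acting is that the figure cannot be verified as written. Like for like with SAP 1.3, 19 looks like a randomized count, and the Evaluable Population in SAP 2.2 needs only one double-blind dose, so evaluable does not mean completer. On that footing, and on the basis that reproduces 80%, power is 67.3%. The planned model can also sit slightly under 70% with all 19 analysed (69% at r = 0, ρ = 0). Raising ρ rescues the 70% but moves the 80% as well, which argues for stating one basis. The wording would cost little.

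The lack of documentation stands. The numerical part does not carry the same weight. Every figure below 70% at 1-sided 0.05 needs ρ at or close to zero. Protocol 5.4 justifies the crossover because each patient acts as their own control and variability falls, which presumes a positive ρ. Zero is therefore the cautious edge, and a positive ρ raises both stated powers, so a claim worded as a minimum is not undermined. The second 10% dropout is an inference: SAP 2.9 was written with enrolment already stopped, and its 19 can as easily mean the patients available for the primary comparison. The 17-completer figures also count dropouts as wholly lost, whereas the likelihood-based model can use period 1 data from a patient lost during the second treatment phase.

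**Conclusion.** The concern does not call for a change. SAP 2.9 leaves out the inputs behind its 70%, but a statistician can supply them from SAP 1.3 and Protocol 10.3.1 and arrive at 71.9%, in line with the claim. This rests on 0.75 in single-score SD units, ρ = 0, 1-sided 0.05 and 19 analysed. The least favourable credible paired t-test reading, 17 completers at ρ = 0, falls 2.7 points short and disappears with a correlation of 0.07. Under the planned model the answer depends on r and ρ, which the documents do not give, and it is below 70% only when ρ is near zero and r is small to moderate.

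The 80% should not be corrected to about 98%: that follows from an SD unit that does not fit the plan's own figure. Enrolment had already ended, so restating the power would alter no design feature, analysis, result or conclusion. It is missing detail that a reader can fill sensibly.
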